9.3 Functional response/change

9.3.1 Change in 6MWT by 50 meters would be considered significant

10.0 Criteria for Removal from the Study

- 10.1** Patient request/consent withdrawal
- 10.2** Noncompliance, including failure to adhere to the study requirements as in the study protocol, and/or lost to follow-up
- 10.3** Investigator decides that, in the interest of the patient, it is not medically acceptable to continue participation in the study
- 10.4** Pregnancy
- 10.5** Patient is unable to tolerate telotristat ethyl following dosage reduction to 250 mg tid
- 10.6** Patient experiences:
 - 10.6.1** Unresolved Grade 3 constipation as graded by the NCI CTCAE v5.0;
 - 10.6.2** Development of severe, persistent, or worsening abdominal pain
 - 10.6.3** Grade 4 toxicity
 - 10.6.4** Suicidal ideation
 - 10.6.5** Death

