6.3.2 Dose Adjustments for adverse events related to the study drug

Adverse Events will be graded as follows (NCI CTCAE version 5.0)

Grade 1 No change in dose
Grade 2 Hold until ≤Grade 1. Resume at same dose level.
Grade 3 Hold until ≤Grade 1. Resume at 1 dose level lower (250 mg tid).
Grade 4 Hold and contact the Primary Investigator

Dose can also be adjusted or discontinued per PI's discretion for patients' safety.

*Patients unable to tolerate 250 mg tid should be discontinued from telotristat ethyl. **Constipation and abdominal pain dose adjustment is different (see below)

6.3.3 Recommended management for the following AEs:**6.3.3.1** Nausea and/or vomiting: treatment with antiemetics**6.3.3.2** Diarrhea: treat underlying cause and/or with antidiarrheal**6.3.3.3** Gastrointestinal toxicity**6.3.3.3.1** Monitor concomitant medication usage**6.3.3.3.2** Constipation (Grade 1 and above): initiate treatment as clinically indicated; examples of therapies include: laxatives, enemas, suppositories, psyllium hydration, over-the-counter (OTC) agents**6.3.3.3.3** Abdominal pain (Grade 1 and above): initiate treatment as clinically indicated; examples of therapies) include: analgesics, anti-gas/bloating agents**6.3.3.3.4** Hold telotristat ethyl for Grade 2 constipation or abdominal pain until \leq Grade 1.**6.3.3.3.5** Discontinue telotristat ethyl for Grade 3 constipation or abdominal pain*(please note this is different than above table)**6.3.3.4** Suicidal ideation: discontinue telotristat ethyl**6.4 Treatment Compliance**

Patients will be asked to bring their unused or unopened bottles of telotristat ethyl to each visit. Patients will be allowed to ship their unused and/or unopened bottles of telotristat ethyl back to PI at MDAnderson if traveling is impossible/restricted. At each visit study site personnel will count returned tablets and reconcile the counts against planned number of doses for that interval. All dosages prescribed and dispensed to the patient, dose modification(s), and missed dose(s), including planned dose interruptions during the study must be recorded. Site personnel are to clarify any discrepancy and record this information.

Patients must maintain at least 70% compliance at clinical visits (3 month interval including allowed window; see section 8 for details) in dosing to be deemed as compliant.

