8.0 Evaluation during Study

- 8.1 Complete history and physical examination done at 3 and 6 months as part of clinical follow-up. (telemedicine technology and language assistant may be used)
**A window of 3 weeks before or after for these visits will be acceptable to accommodate for patient convenience.
- 8.2 CBC with differential, Liver panel (to include AST, ALT, bilirubin, albumin), basic metabolic panel (Sodium, potassium, bicarbonate, chloride, BUN, creatinine, glucose) done at 3 and 6 month (**-asterisk- labs and tests maybe done 3 weeks prior or up to 3 weeks after clinical follow-up date)
- 8.3 ECG done at 3 and 6 months within 6 weeks of clinical visit**
- 8.4 Pregnancy test for females of childbearing age within one week
- 8.5 MDASI done at 3 and 6 months (telemedicine technology and language assistant may be used;can be done within 6 weeks of clinical follow-up)
- 8.6 Echocardiography with a 2D transthoracic echocardiography (2D TTE), 3-dimensional echocardiography (3D TTE), and myocardial strain of the left and right ventricle to be done at 3 and 6 months for those patients with carcinoid heart disease and with carcinoid syndrome and high suspicion of carcinoid heart disease (CHD group), such as those with clinical features or increased NT-proBNP (> 260) mg/ml and/or 5-HIAA levels (24 hr urine 5-HIAA > 100 mg). (**- asterisk- labs and tests maybe done 3 weeks prior or up to 3 weeks after clinical follow-up date
- 8.7 Echocardiography will be done at 6 months in patients with carcinoid syndrome (CS group) who do not have high suspicion for carcinoid heart disease

8.8 Plasma 5-HIAA collection at 3 and 6 months (**-asterisk- labs and tests maybe done 3 weeks prior or up to 3 weeks after clinical follow-up date) (it will be kept frozen in Cryogene lab and will be transferred to Frontage Lab for analysis. More information is included in the lab manual.)

8.9 Cardiac biomarkers to include: N-terminal pro B-type natriuretic peptide (NT-proBNP) and high sensitivity troponin T (HS-troponin T) at 3 and 6 months (**-asterisk- labs and tests maybe done 3 weeks prior or up to 3 weeks after clinical baseline/follow-up date)

8.10 6 minute walk test (6MWT) where distance is recorded in meters at 3 and 6 months (**-asterisk- labs and tests maybe done 3 weeks prior or up to 3 weeks after clinical follow-up date)

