11.2 Statistical Analysis Plan

We will analyze two analysis sets, including modified intention-to-treat and per protocol analysis sets. Modified intention-to-treat analysis set will include all patients who were randomized and started a study treatment, regardless of whether they received treatment as planned. Per protocol analysis set will include all patients who received treatment as planned.

Patient baseline characteristics and outcome variables (primary endpoint and secondary endpoints (absolute changes and percent changes for continuous endpoints)) will be summarized by study arm, using mean (standard deviation (SD)) or median (inter quartile range (IQR)) for continuous variables and frequency (%) for categorical variables. Repeatedly measured variables will be summarized using descriptive statistics by study arm and by time point (baseline, 3 months, and 6 months). The mean percent

change in NT-proBNP at 6 months from baseline will be estimated in each arm along with the standard deviation. The mean percent change in NT-proBNP will be compared between 2 arms by two-sample t-test. Linear regression model will be used to compare the 2 arms in the mean percent change, adjusting for stratification factors. Those without 3-months or 6-months NT-proBNP may be imputed, using last observation carried forward method or other methods.

Compliance is defined as the total number of medications taken divided by the total number of medications provided during 6 month treatment period. The proportion of patients maintaining at least 70% compliance will be estimated in each arm. Proportion of patients experiencing each type of side effects will be estimated in each arm along with 95% confidence interval (CI). The change from baseline to 3 months and the change from baseline to 6 months in variables described in secondary objectives will be compared within each arm by paired t-test or Wilcoxon signed-rank test for continuous variables and Mantel-Haenszel test for categorical variables. Generalized linear mixed effects models will be used to compare two arms in repeatedly measured outcomes over time. P-values less than 0.05 will indicate statistical significances. SAS 9.4 (Cary, NC) and other relevant software will be used for statistical analysis.

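### Section 10 removes patients from the study for treatment-related reasons, and no text keeps the month-6 NT-proBNP that the modified ITT analysis needs

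*Combined protocol and SAP*

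**What the plan says.** Section 10 is headed as criteria for removal from the study. Its list includes noncompliance (10.2), intolerance of the reduced dose (10.5: "Patient is unable to tolerate telotristat ethyl following dosage reduction to 250 mg tid"), unresolved Grade 3 constipation (10.6.1), abdominal pain (10.6.2: "Development of severe, persistent, or worsening abdominal pain"), Grade 4 toxicity (10.6.3) and suicidal ideation (10.6.4).

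Sections 6.3.2 and 6.3.3 deal with the same adverse events by acting on the drug. For constipation and abdominal pain the rules are "Hold telotristat ethyl for Grade 2 constipation or abdominal pain until" Grade 1 or lower and, one step up, "Discontinue telotristat ethyl for Grade 3 constipation or abdominal pain". For intolerance the rule is "Patients unable to tolerate 250 mg tid should be discontinued from telotristat ethyl". Section 6.3.1.2 defines discontinuation as withdrawal from the drug, so the protocol itself separates stopping drug from leaving the study.

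Section 11.2 defines the modified ITT set as "all patients who were randomized and started a study treatment, regardless of whether they received treatment as planned". The primary endpoint is the percent change in NT-proBNP from baseline to month 6. Section 8.9 schedules "N-terminal pro B-type natriuretic peptide (NT-proBNP) and high sensitivity troponin T (HS-troponin T) at 3 and 6 months", and the schedule in 8.13 has no early-withdrawal sample. For missing values, 11.2 says: "Those without 3-months or 6-months NT-proBNP may be imputed, using last observation carried forward method or other methods". Section 11.1 replaces drop-outs until 52 patients have the endpoint.

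**The concern.** A patient who stops drug because of toxicity or poor adherence belongs to the modified ITT set, and the month-6 NT-proBNP of that patient is part of what the set is meant to describe. If the patient is removed from the study at the same moment, nothing in the plan secures that value. Removal follows randomisation and can depend on the drug or on the disease, so values lost this way are unlikely to be missing at random and may differ between arms.

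The modified ITT comparison would then rest either on an imputation rule that has not been fixed or on the patients who tolerated and took their assigned treatment. The second case is close to the per-protocol set that the modified ITT analysis is meant to complement.

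**Working it through.** **Step 1. Match each removal criterion with the drug rule for the same event.**

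| Removal from study | Drug rule elsewhere |
|---|---|
| 10.2 noncompliance | 6.4 defines 70% compliance; 11.2 keeps the patient in the modified ITT set regardless |
| 10.5 cannot tolerate 250 mg tid | 6.3.2: discontinue drug |
| 10.6.1 unresolved Grade 3 constipation | 6.3.3.3.5: discontinue drug |
| 10.6.2 abdominal pain | 6.3.3.3.4 and 6.3.3.3.5: hold at Grade 2, discontinue at Grade 3 |
| 10.6.3 Grade 4 toxicity | 6.3.2: hold and contact the investigator |
| 10.6.4 suicidal ideation | 6.3.3.4: discontinue drug |

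**Step 2. Look for any text that keeps the sample.** Sections 12.2 and 12.5 follow adverse events after the last dose. Section 8.12 collects hospitalisation, death and routine data, but names neither NT-proBNP nor removed patients. No text asks for the month-6 NT-proBNP after removal.

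**Step 3. Reproduce the plan's figures (11.1).**
- Evaluable: 52, so 26 per arm at 1:1. Power at effect size 0.8 (20/25), two-sided 0.05, t-test: 80.7%, against 80% stated.
- Standard error of the difference: 25 × √(2/26) = 6.93.
- Top-up: drop-out 16/44 = 36.4%; 14/(1 − 16/44) = 22; less the 3 not yet randomised = 19. This matches.
- Treated patients who had completed or withdrawn: 28 + 6 = 34. Lost before month 6: 6/34 = 17.6%.

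**Step 4. Illustrate the effect on the primary comparison.** Enrolment continues until 52 patients have the endpoint, so removed patients come on top of the 26 completers per arm. Assume that k = 1 to 3 telotristat patients are removed before month 3, and that the change they would have shown is m = 10% to 30% in size. Both k and m are assumptions; the documents give neither.

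*Baseline carried forward (0% change).* Shift in the arm mean = k × m/(26 + k).
- k = 1, m = 10: 10/27 = 0.4 points.
- k = 3, m = 30: 90/29 = 3.1 points.

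The two-sided error was simulated with no true difference: normal data, SD 25, both arms with mean m, k extra telotristat patients set to 0, two-sample t-test at 0.05.

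| | m = 10 | m = 20 | m = 30 |
|---|---|---|---|
| k = 1 | near 5% | near 5% | near 5% |
| k = 3 | 5.3% | 5.8% | 6.7% |

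*Removed patients left out and replaced.* If stopping drug returns a patient to placebo level, a 20-point effect in completers becomes 20 × 26/(26 + k) for all treated.
- k = 1: 20 × 26/27 = 19.3.
- k = 3: 20 × 26/29 = 17.9.

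**Step 5. Illustrate the effect on enrolment.** Suppose 2 of the 6 treated withdrawals had kept a month-6 value. Completion is then 30/34, and 11 of the 13 still in follow-up are expected to complete (13 × 30/34 = 11.5, rounded down as the plan does). That gives 41, so 11 more are needed. Drop-out is 14/44 = 31.8%; 11/(1 − 14/44) = 16.1, rounded up to 17; less 3 = 14 additional patients instead of 19. The documents do not say that any of the six left under these criteria.

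**The case against.** The strongest objection is that nothing shows harm. The plan gives no rate for any of these removals, no reasons for the six treated withdrawals and no arm for them. The upper figures in step 4 need three early removals, all on telotristat, all carried forward from baseline, and a 30% mean change in both arms. The only comparative safety evidence in the document (11.3) reports a similar overall incidence of treatment-related adverse events across groups, with serious events in 19.2% on placebo, 4.0% on 250 mg and 12.0% on 500 mg. It is not specific to these criteria, but it gives no support to an excess of removals on telotristat. All of this stands, and it limits the size of the point.

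It can also be said that imputation and replacement are already planned. They do not close the gap: imputation is optional with an open method, and replacement brings in different patients.

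Three stronger readings are tempting, and the documents support none of them.
- A reader might infer that abdominal pain in particular is driving the losses. No loss is attributed to pain, and the gap is the same across section 10.
- A reader might infer that the result is already biased towards or against telotristat. Neither the arm nor the direction can be known from the plan.
- A reader might take 10.6.2 to force removal for any rise in pain, because it gives no grade. The neighbouring 10.5 and 10.6.1 suggest that failure after management is meant, and a broad safety trigger is a legitimate choice. At most this needs clarifying.

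**Conclusion.** The point holds as a gap across section 10. Following the written rules loses primary-endpoint values through events after randomisation, in patients whom the modified ITT set is defined to include, and no text secures the sample.

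The size of any bias is unknown. Under the stated assumptions it is small: a shift of 0.4 to 3.1 points against a planned difference of 20 and a standard error of about 6.9, a two-sided error of about 5.3% to 6.7% with three such patients and near 5% with one, or a diluted effect of 17.9 to 19.3 instead of 20. The case for acting rests on the low cost of the remedy and on an observed loss of 17.6% of treated patients from all causes, not on a demonstrated distortion.

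**What to change.** At the head of section 10, state that 10.2 (noncompliance with study drug), 10.5 and 10.6.1 to 10.6.4 stop study drug only. Unless the patient withdraws consent, is lost to follow-up, or the investigator decides otherwise under 10.3, the patient stays in follow-up for the scheduled 3- and 6-month NT-proBNP. Say explicitly that outside laboratory results are accepted for these samples. Section 7 already allows outside results, and its footnote on follow-up dates suggests that the allowance may reach beyond baseline.

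In 11.2, state that an observed month-6 value is used in the modified ITT analysis whatever drug was taken.

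The cost is two short text changes and at most two already scheduled blood samples for each patient who stops drug. No safety stop is narrowed. The benefit reaches only patients not yet removed: at the drop-out review these included 13 treated patients still in follow-up, 3 awaiting randomisation and the 19 still to be enrolled.

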11.0 Statistical Consideration

11.1 Sample Size Justification

Primary endpoint is the percent change in NT-proBNP at 6 months from baseline, which is defined as the absolute change divided by the baseline value multiplied by 100. A total sample size of 60 (30 in each group) will be enrolled, accounting for ~13% drop out rate to have 52 subjects with a primary endpoint. Enrolled participants who were dropped out of study will be replaced with additional participants if more than 13% participants were dropped out of the study. A sample size of 30 in each group produces a 95% confidence interval equal to the sample mean change in NT-proBNP plus or minus 10 when the estimated standard deviation is 25, accounting for ~13% drop out rate. There is no preliminary data and there are no similar studies to obtain preliminary estimates for the percent change in NT-proBNP in any of 2 arms.

Therefore, the sample size calculation was performed based on an effect size of 0.8, which is considered as large. Group sample sizes of 30 and 30 achieve 80% power to detect a standard effect size of 0.8 (for example, mean percent difference of 20 when the standard deviation of 25) with a significance level (alpha) of 0.05 using a two-sided two-sample t-test, accounting for ~13% drop out rate. PASS 2005 (Hintze, J. (2004). NCSS and PASS. Number Cruncher Statistical Systems. Kaysville, Utah.

www.ncss.com) was used for the sample size calculation. The caveat is that if the true effect size is smaller than the effect used in power calculation then the calculated sample size will not be enough to achieve 80% power. In case the study turns to be not significant but promising in this setting, these data can be used as preliminary estimates to design a bigger trial.

After enrolling 60 subjects, we evaluated the observed drop-out rate. Three subjects were not randomized yet. Six-month follow-up was not reached for 13 subjects. Sixteen subjects were dropped out of the study (withdrawn prior to randomization (n=6), randomized but withdrawn prior to receiving study treatment (n=4), and randomized, treated, but withdrawn prior to 6-month follow-up (n=6)). Drop-out rate among those who were enrolled, excluding those not reaching 6-month follow-up and those not randomized yet, is 36% (16/44). Since the drop-out rate is higher than 13%, we will enroll additional subjects to replace those who dropped out of the study.

Among those who received the study drug, 28 subjects have completed 6-month follow-up; 13 subjects were not reached 6-month follow-up yet; 6 subjects were withdrawn prior to 6-month follow-up. 6-month follow-up completion rate among those who received the study drug and reached 6-month follow-up visit is 82% (28/34). At this rate, we expect that 10 of 13 not reaching 6-month will complete 6-month follow-up. To have 52 subjects with a primary endpoint, we still need 14 (i.e., 52-38) additional subjects with a primary endpoint.

Applying the drop-out rate of 36%, we may need to enroll 19 additional subjects in addition to 3 subjects who were not randomized yet. As we enroll additional subjects in the study, we will monitor the number of subjects who complete 6-month follow-up with a primary endpoint. Our goal is to have 52 subjects with a primary endpoint. We will stop enrolling additional subjects once the number of subjects who complete 6-month follow-up with a primary endpoint reaches 52.

If needed, we will evaluate the observed drop-out rate and re-estimate the number of

additional subjects to enroll to have 52 subjects with a primary endpoint after enrolling 19 additional subjects,

11.2 Statistical Analysis Plan

We will analyze two analysis sets, including modified intention-to-treat and per protocol analysis sets. Modified intention-to-treat analysis set will include all patients who were randomized and started a study treatment, regardless of whether they received treatment as planned. Per protocol analysis set will include all patients who received treatment as planned.

Patient baseline characteristics and outcome variables (primary endpoint and secondary endpoints (absolute changes and percent changes for continuous endpoints)) will be summarized by study arm, using mean (standard deviation (SD)) or median (inter quartile range (IQR)) for continuous variables and frequency (%) for categorical variables. Repeatedly measured variables will be summarized using descriptive statistics by study arm and by time point (baseline, 3 months, and 6 months). The mean percent

change in NT-proBNP at 6 months from baseline will be estimated in each arm along with the standard deviation. The mean percent change in NT-proBNP will be compared between 2 arms by two-sample t-test. Linear regression model will be used to compare the 2 arms in the mean percent change, adjusting for stratification factors. Those without 3-months or 6-months NT-proBNP may be imputed, using last observation carried forward method or other methods.

Compliance is defined as the total number of medications taken divided by the total number of medications provided during 6 month treatment period. The proportion of patients maintaining at least 70% compliance will be estimated in each arm. Proportion of patients experiencing each type of side effects will be estimated in each arm along with 95% confidence interval (CI). The change from baseline to 3 months and the change from baseline to 6 months in variables described in secondary objectives will be compared within each arm by paired t-test or Wilcoxon signed-rank test for continuous variables and Mantel-Haenszel test for categorical variables. Generalized linear mixed effects models will be used to compare two arms in repeatedly measured outcomes over time. P-values less than 0.05 will indicate statistical significances. SAS 9.4 (Cary, NC) and other relevant software will be used for statistical analysis.

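### Section 11.2 does not fix the deciding analysis set or the rule for missing NT-proBNP, with about 12 of 64 treated patients expected to lack a 6-month value; the mixed model it already names should carry the primary contrast in mITT

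*Combined protocol and SAP*

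**What the plan says.** The primary endpoint is percent change in NT-proBNP from baseline to 6 months (sections 2.0 and 11.1). Section 11.2 gives these elements:

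- Sets: "We will analyze two analysis sets, including modified intention-to-treat and per protocol analysis sets". On the first, "Modified intention-to-treat analysis set will include all patients who were randomized and started a study treatment". Per protocol is everyone treated as planned, with no operational rule. Neither set is named as deciding.
- Tests: "The mean percent change in NT-proBNP will be compared between 2 arms by two-sample t-test", and "Linear regression model will be used to compare the 2 arms in the mean percent change, adjusting for stratification factors".
- Missing values: "Those without 3-months or 6-months NT-proBNP may be imputed, using last observation carried forward method or other methods".
- Repeated measures: "Generalized linear mixed effects models will be used to compare two arms in repeatedly measured outcomes over time". This is not tied to the 6-month primary contrast.

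Neither the regression nor the mixed model is stated to include baseline NT-proBNP.

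Section 11.1 powers the t-test on 52 patients with the endpoint and stops enrolment at that number. For patients treated so far it reports: "28 subjects have completed 6-month follow-up; 13 subjects were not reached 6-month follow-up yet; 6 subjects were withdrawn prior to 6-month follow-up". NT-proBNP is measured at baseline, 3 and 6 months (sections 7.9, 8.9 and 8.13).

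**The concern.** A patient who starts treatment and leaves before month 6 belongs to mITT but has no primary endpoint. Section 11.2 does not settle whether that patient is left out, carried forward or handled in some other way, so the deciding test could rest on about 52 patients or about 64.

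Both obvious routes have a defect. LOCF assigns exactly 0% change to anyone who leaves before month 3, which dilutes a real effect. If NT-proBNP drifts and drop-out differs by arm, it can also create a false one. Using observed values alone turns mITT into a completer analysis, which flatters an arm whose worsening patients leave. If the choice is made after results are seen, the primary p-value no longer has a fixed meaning.

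**Working it through.** **1. The plan's own figures.** Two-sided alpha 0.05, difference 20, SD 25, so effect size 20/25 = 0.8. The noncentral t requires 25.5, so 26, per arm, and 26 per arm gives 80.7% power. 52/(1 − 0.13) = 59.8, so 60 enrolled. The re-estimate is 14/(1 − 0.36) = 21.9, so 22 = 19 + 3. All reproduce.

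**2. Patients affected (counts from section 11.1).**
- Treated so far: 28 + 13 + 6 = 47.
- Expected completers among them: 28 + 10 = 38.
- Still needed: 52 − 38 = 14, which takes 14/(28/34) = 17 more treated.
- Total treated: 47 + 17 = 64. Without a 6-month value: 64 − 52 = 12 (19%).

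This is a projection; the exact 95% CI for 28/34 is 65% to 93%. For 52 completers, 90% completion means 6 missing of 58, and 75% means 18 of 70.

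**3. LOCF and a true 20-point difference.** Assume equal drop-out by arm, with 6 of the 12 leavers going before month 3 (carried effect 0) and 6 after.
- Half the effect present at month 3: 20 × (52 + 6 × 0.5)/64 = 17.2.
- All of it present: 20 × (52 + 6)/64 = 18.1.
- If all 12 leave before month 3: 20 × 52/64 = 16.25.

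**4. False positives with no drug effect (simulation).** Assumptions: 32 treated per arm for 6 against 6 leavers; half of patients with heart disease; baseline medians 1,149 and 101 pg/ml (section 3.4) with log SD 0.9; log change with SD s and correlation 0.6 between months 3 and 6; half of leavers before month 3. SD of percent change is 100 × exp(s²/2) × √(exp(s²) − 1), about 25, 60 and 130 for s = 0.243, 0.5 and 0.8. Only the first matches the plan; the others are assumed.

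| Drop-out (drug vs placebo) | Observed-only t-test | LOCF t-test | Mixed model on percent change |
|---|---|---|---|
| Random, 6 vs 6 | 4–5% | 4–5% | 4–5% |
| Random, 10 vs 2, both arms rise 20% | 4–5% | about 8%, 6%, 5% at s = 0.243, 0.5, 0.8 | 4–5% |
| Late drug-arm leavers have the largest 3-month rise, 6 vs 6 | 7–8% | about 5% | 4–5% |
| The same, 10 vs 2 | 10–12% | 5–7% | 4–5% |

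In the third row the observed-only estimate is 3 to 16 points in the drug's favour, LOCF is 2 to 15 points against it, and the mixed model's bias is under 3 points. With independent measurement error at each visit instead, observed-only gives 6–7% (6 vs 6) and 7–9% (10 vs 2).

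The second-row LOCF figure depends on the set-up. At an SD of about 25, other reasonable versions gave 6 to 7%, and 8.5% (half of carried values are baseline) to 13% (all are). At 8 vs 4 leavers it is 4 to 7%.

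**5. Power.** At a log effect of 0.8 × s the observed-only t-test has 80%, 76% and 69% power at s = 0.243, 0.5 and 0.8. The mixed model on percent change is within about 1 to 2 points of it.

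**The case against.** The strongest reply is that section 11.1 already answers the question. It powers a t-test on 52 patients with the endpoint, replaces those who drop out and stops at 52 completers. That points to an observed-value t-test as the main analysis, with imputation as a supplement. The t-test matches the endpoint and is valid under random drop-out. LOCF costs little power (2 points lower to 5 higher than observed-only). The 10 against 2 split and the informative drop-out are assumptions, since the documents give no drop-out by arm.

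All of that stands as fact. It does not close the gap: the reading must be inferred, it sits beside an mITT definition that includes everyone who started treatment, and it leads to a completer analysis.

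Three stronger readings are tempting, and the documents do not support them.

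- *A reader might infer that the plan has no check on its raw percent-change t-test.* Section 11.2 has a regression adjusted for the stratification factors, which include heart disease status (section 6.2.1), and a mixed-model sentence that can cover NT-proBNP. What is missing is a stated baseline term and a link to the month-6 contrast.
- *A reader might infer that the false-positive rate is already 7 to 9%, because any of the sets or LOCF could win.* That assumes any significant result counts, and no such rule is stated.
- *A reader might infer that a log scale is needed.* At the plan's SD a log mixed model and the t-test both have 80% power. If percent change is truly normal, the log model loses 2 to 6 points. Starting from the plan's expected result (p = 0.006), one placebo patient at −90% moves p to 0.038 raw but 0.35 on the log scale. One drug patient at +100% favours the log scale (0.07 raw, 0.04 log). In a set-up where change depends on baseline, log analysis with baseline reached 88% against 80%, but log change without baseline gave only 82%, so most of that gain came from the baseline term.

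**Conclusion.** The point holds in this form: the deciding set is unnamed, the missing-data rule is optional and open, and about 12 of 64 treated patients (range 6 of 58 to 18 of 70) are exposed to that choice. The count follows from section 11.1's own rates.

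The harm from LOCF is mainly dilution, about 2 to 3 points of a 20-point difference if half of leavers go before month 3. Excess false positives need very unequal drop-out together with drift. Observed-only is not a safe default either, because it does worst when worsening patients leave. A baseline-adjusted repeated-measures model on data already scheduled held 4 to 5% in every case examined. The simulated sizes rest on assumed variability and drop-out patterns, since section 11.1 states that no preliminary data exist. This should be corrected before unblinding, but it does not make the planned t-test invalid.

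**What to change.** Amend section 11.2 before unblinding:

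1. Name mITT as the deciding set and per protocol as supportive, with an operational definition of the latter.
2. Delete LOCF and the open alternative. Handle missing values with the mixed model already named, fitted in mITT to percent change at months 3 and 6 on arm, visit, arm-by-visit, log baseline NT-proBNP, age group and heart-disease stratum. Make the month-6 arm difference the deciding contrast.
3. Keep the two-sample t-test on observed 6-month values as supportive, labelled as a completer analysis. Label the strata-adjusted regression supportive too.
4. Optional: the same model on log NT-proBNP as a sensitivity analysis, and a check on departures from missing at random.

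Cost: wording only. The endpoint, the target of 52 and the visit schedule do not change. The deciding test is no longer the plain t-test of section 11.1, which needs a sentence there, and power may be about 1 to 2 points lower. The model assumes missing at random, and patients who leave before month 3 add almost nothing to it.
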